## **8.2. Laboratory Test Abnormalities**

Laboratory abnormalities that constitute an AE in their own right (considered clinically meaningful, induce clinical signs or symptoms, require concomitant therapy, or require changes in study drug) should be recorded on the Adverse Event form in the eCRF. Whenever possible, a diagnosis rather than a symptom should be provided (eg, "anemia" instead of "low hemoglobin"). Laboratory abnormalities that meet the criteria for AEs should be followed until they have returned to normal or an adequate explanation of the abnormality is found. When an abnormal laboratory test result corresponds to a sign or symptom of a previously reported AE, it is not necessary to separately record the laboratory test result as an additional event.

Laboratory abnormalities that do not meet the definition of an AE should not be reported as AEs. A Grade 3 or 4 (severe) AE does not automatically indicate an SAE unless it meets the definition of serious, as defined in Section 8.3.1. A dose modification for the laboratory abnormality may be required (see Section 5.4) and should not contribute to the designation of a laboratory test abnormality as an SAE.

## **8.3. Serious Adverse Events**

### **8.3.1. Definitions**

An SAE is defined as an event that meets at least 1 of the following criteria:

- Is fatal or life-threatening.
- Requires inpatient hospitalization or prolongation of existing hospitalization, unless hospitalization is a result of:
  - A routine treatment or monitoring of the studied indication not associated with any deterioration in condition.
  - An elective surgery or preplanned treatment for a pre-existing condition that is unrelated to the indication under study and has not worsened since signing the ICF.
  - A treatment on an emergency outpatient basis for an event not fulfilling any of the definitions of a SAE and not resulting in hospital admission.
  - Any social reasons and respite care, in the absence of any deterioration in the subject's general condition.
- Results in persistent or significant disability, incapacity, or a substantial disruption of a person's ability to conduct normal life functions.
- Constitutes a congenital anomaly or birth defect.
- Is considered to be an important medical event or a medically significant event that may not result in death, be immediately life-threatening, or require hospitalization but may be considered serious when, based on appropriate medical judgment, the event may jeopardize the subject or may require medical or surgical intervention to prevent 1 of the outcomes listed above.

### **8.3.2. Reporting**

Every SAE, regardless of suspected causality (eg, relationship to study drug(s) or study procedure or disease progression), occurring after the subject has signed the ICF through the last study visit (or 30 days after the last dose of study drug, whichever is later) must be reported to the sponsor (or designee) within **24 hours** of learning of its occurrence, unless otherwise specified by the Protocol. Any SAEs occurring more than 30 days after the last dose of study drug should be reported to the sponsor or its designee only if the investigator suspects a causal relationship to the study drug.

Information about all SAEs is collected and recorded on the Adverse Event form of the eCRF. The investigator must assess and record the causal relationship of each SAE to the study treatment.

The investigator must also complete the Incyte Serious Adverse Event Report Form, in English, and send the completed and signed form to the sponsor or designee within 24 hours of becoming aware of the SAE. The investigator must provide a causality assessment, that is, assess whether there is at least a reasonable possibility that the SAE is related to the study treatment: suspected (yes) or not suspected (no). Refer to the Incyte Reference Guide for Completing the Serious Adverse Event Report Form.

The contact information of the sponsor's study-specific representatives is listed in the investigator manual provided to each site. The original copy of the SAE Report Form and the confirmation sheet must be kept at the study site.

Investigational site personnel must report any new information regarding the SAE within 24 hours of becoming aware of the information in the same manner that the initial SAE Report Form was sent. Follow-up information is recorded on an amended or new SAE Report Form, with an indication that it is follow-up to the previously reported SAE and the date of the original report. The follow-up report should include information that was not provided on the previous SAE Report Form, such as the outcome of the event (eg, resolved or ongoing), treatment provided, action taken with study drug because of the SAE (eg, dose reduced, interrupted, or discontinued), or subject disposition (eg, continued or withdrew from study participation). Each recurrence, complication, or progression of the original event should be reported as follow-up to that event, regardless of when it occurs.

If the SAE is not documented in the IB for the study drug (new occurrence) and is thought to be related to the sponsor's study drug, the sponsor or its designee may urgently require further information from the investigator for reporting to health authorities. The sponsor or its designee may need to issue an Investigator Notification (IN) to inform all investigators involved in any study with the same drug that this SAE has been reported. Suspected Unexpected Serious Adverse Reactions (SUSARs) will be collected and reported to the competent authorities and relevant ethics committees in accordance with Directive 2001/20/EC, or as per national regulatory requirements in participating countries.

Upon implementation of Amendment 4, all SAEs regardless of causal relationship will be reported as described above.

#### 8.4. Adverse Events of Special Interest

Specific adverse events, or groups of adverse events, will be followed as part of standard safety monitoring activities. These events (regardless of seriousness) will be reported per the SAE reporting timelines (see Section 8.3.2).

- $ALT \geq 5 \times ULN$
- $AST \geq 5 \times ULN$
- Colitis
- Diarrhea  $\geq$  Grade 2
- Rash  $\geq$  Grade 2
- Intestinal perforation
- Pneumonitis
- *Pneumocystis jirovecii* infection
- CMV infection
- Herpes simplex virus infection
- Varicella zoster virus infection
- Exfoliative dermatitis

#### 8.5. Pregnancy

Pregnancy, in and of itself, is not regarded as an AE unless there is suspicion that study drug may have interfered with the effectiveness of a contraceptive medication or method. When a pregnancy has been confirmed in a subject during maternal or paternal exposure to study drug, the following procedures should be followed in order to ensure subject safety:

- The study drug must be discontinued immediately (female subjects only; see Section 5.4 for the maximum permitted duration of study drug interruption).
- The investigator must complete and submit the Incyte Clinical Trial Pregnancy form to the sponsor or its designee within **24 hours** of learning of the pregnancy.

Data on fetal outcome and breastfeeding are collected for regulatory reporting and drug safety evaluation. Follow-up should be conducted for each pregnancy to determine outcome, including spontaneous or voluntary termination, details of the birth, and the presence or absence of any birth defects, congenital abnormalities, or maternal and/or newborn complications, by following until the first well-baby visit. Pregnancy should be recorded on a Clinical Trial Pregnancy form and reported by the investigator to the sponsor or its designee. Pregnancy follow-up information should be recorded on the same form and should include an assessment of the possible causal relationship to the sponsor's study drug to any pregnancy outcome, as well as follow-up to the first well-baby visit or the duration specified in local regulations, whichever is later. Refer to the Incyte Reference Guide for Completing the Clinical Trial Pregnancy Form.

**Any SAE occurring during pregnancy must be recorded on the SAE report form and submitted to the sponsor or designee.**

## **8.6. Warnings and Precautions**

Special warnings or precautions for the study drug, derived from safety information collected by the sponsor or its designee, are presented in the Investigator's Brochure (INCB050465 IB). Additional safety information collected between IB updates will be communicated in the form of Investigator Notifications (INs). Any important new safety information should be discussed with the subject during the study, as necessary. If new significant risks are identified, they will be added to the ICF.

## **8.7. Independent Data Monitoring Committee**

An IDMC will be formed and will consist of qualified individuals who are not involved with the conduct of the study. The establishment, composition, roles, duties, and responsibilities of the IDMC are addressed in the approved IDMC charter.

## **8.8. Product Complaints**

The sponsor collects product complaints on study drugs and drug delivery systems used in clinical studies in order to ensure the safety of study participants, monitor quality, and facilitate process and product improvements.

All product complaints associated with material packaged, labeled, and released by the sponsor or its designee will be reported to the sponsor. All product complaints associated with other study material will be reported directly to the respective manufacturer.

The investigator or his/her designee is responsible for reporting a complete description of the product complaint via email or other written communication to the sponsor contact or respective manufacturer as noted in the packaging information. Any AE associated with a product complaint should be reported as described in Section 8.1.2 of this Protocol.

If the investigator is asked to return the product for investigation, he/she will return a copy of the product complaint communication with the product.

## 9. STATISTICS

### 9.1. Study Populations

[figure not shown]
The full analysis set includes all subjects enrolled in the study who received at least 1 dose of INCB050465. The full analysis set will be used for the summary of demographics, baseline characteristics, subject disposition, and analyses of all efficacy data.

The per protocol (PP) population includes all subjects in the full analysis set who were sufficiently compliant with the Protocol. The following procedures will be performed to identify those subjects who are to be excluded from the PP population before the database freeze:

- Clinical review of Protocol deviations/violations
- Clinical review of concomitant medications as defined in Section 5.6 of the Protocol
- Clinical review of the dose administration and drug accountability listing

The determination of subjects being considered for exclusion from the PP population by the clinical team will be prepared and signed before database freeze.

The safety population includes all subjects enrolled in the study who received at least 1 dose of INCB050465. This population will be used for all safety analyses.

### 9.2. Selection of Sample Size

The study will enroll 100 subjects into Group A. If the true ORR is 0.50, then there is approximately 90% probability of observing the lower bound of the 95% CI of the ORR  $\geq 35\%$ .

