
Statistical Methods: Data from Group A and Group B will be analyzed separately. Response data will be analyzed when all subjects have received at least 1 postbaseline disease assessment, or have progressed, withdrawn from the study, or died. There will not be any statistical comparison between the 2 groups.
 
Sample Size:
 
Group A: 100 subjects will be enrolled. If the true ORR is 0.50, then there is about 90% probability of observing the lower bound of the 95% confidence interval of <math>ORR \geq 35\%</math>.
 
Group B: Up to 20 subjects will be enrolled. There is 87% probability of observing <math>\geq 6</math> responders in 20 subjects [REDACTED].
 
Primary Analysis: Group A only: The ORR as determined by the IRC and its 95% exact binomial confidence intervals (CIs) will be calculated. The ORR as determined by the investigators and its 95% CI will be provided as a sensitivity analysis.
 
Secondary Analyses:
 
Group A: The Kaplan-Meier estimation of median DOR and PFS (per IRC) and OS will be presented with respective 95% CIs.

All safety data, including AEs, laboratory data, vital signs, and ECGs, will be summarized descriptively.

**Level of Significance:** There will not be any statistical comparison between the 2 groups. Within each group, 2-sided 95% CIs will be reported for all analyses when appropriate.

**Interim Analysis:** An interim futility analysis is planned for Group A. The analysis will be conducted when 40 subjects have been treated and evaluated for response or have permanently discontinued study treatment because of disease progression, withdrawal of consent, or death. Group A will be terminated for futility if  $\leq 13$  of the 40 subjects responded (ie, CR/CMR or PR/PMR) based on assessments provided by the IRC. The futility boundary is calculated using a spending function of HSD(-4). No formal futility analysis will be conducted for Group B.

**Independent Data Monitoring Committee:** An independent Data Monitoring Committee (IDMC) will be established and will review data at predetermined intervals as specified in the IDMC charter.

5.1.1.	Subject Numbering and Treatment Assignment.....	26
5.1.2.	Randomization and Blinding.....	27
5.2.	INCB050465.....	27
5.2.1.	Description and Administration.....	27
5.2.2.	Supply, Packaging, and Labeling.....	27
5.2.3.	Storage.....	28
5.2.4.	Instruction to Subjects for Handling INCB050465.....	28
5.3.	Treatment Compliance.....	28

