### 9.3. Level of Significance

There will not be any statistical comparison between the 2 groups. Within each group, 2-sided 95% CIs will be reported for all analyses when appropriate.

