## **9.4. Statistical Analyses**

### **9.4.1. Efficacy Analyses**

#### **9.4.1.1. Primary Efficacy Analyses**

Objective response rate is defined as the percentage of subjects with a CR/CMR or PR/PMR as determined by revised response criteria for DLBCL ([Cheson et al 2014](#)).

The ORR as determined by the IRC and its 95% exact binomial CIs will be calculated for subjects in Group A. This is considered the primary efficacy analysis of the study.

The ORR as reported by the investigator and its 95% exact binomial CIs will also be calculated for subjects in Group A.

Response data will be analyzed when all subjects have received at least 1 postbaseline disease assessment, or have progressed, withdrawn from the study, or died.

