### **9.5. Analyses for the Independent Data Monitoring Committee**

Preplanned analyses of safety will be provided to the IDMC as specified in the IDMC charter. In addition, the IDMC will make recommendations to the sponsor at the planned interim futility analysis in Group A (see Section 9.6). The process by which the IDMC will make recommendations and decisions will be documented in the IDMC charter.

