**1. Synopsis; Section 4.1, Overall Study Design; Section 9.2, Selection of Sample Size; Section 9.6, Interim Analysis**

**Description of change:** An interim futility analysis has been added. The analysis is planned when the first 40 subjects in Group A have been treated and have been evaluated for response or have permanently discontinued study treatment because of disease progression, withdrawal of consent, or death. Group A of the study will be terminated for futility if  $\leq 13$  of the 40 subjects have responded (ie, complete response [CR]/complete metabolic response [CMR] or partial response [PR]/partial metabolic response [PMR]) based on assessments provided by the independent review committee; otherwise the study will continue. A timely assessment of response will be performed to avoid the risk of overenrollment. No formal futility analysis will be conducted for Group B. Section 9.2 (Selection of Sample Size) was updated to be consistent with the numbers used in the added interim analysis.

**Rationale for change:** Requested by the FDA.

**2. Synopsis; Section 4.1, Overall Study Design; Section 4.6, Study Termination; Section 8.7, Independent Data Monitoring Committee; Section 9.5, Analyses for the Independent Data Monitoring Committee**

**Description of change:** An independent Data Monitoring Committee (IDMC) was included in the study to review safety and perform the futility analysis.

**Rationale for change:** Requested by the FDA.

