7.1. Efficacy Hypotheses

Not applicable.

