9. INTERIM ANALYSES

9.1. Overview of Interim Analyses

An interim futility analysis is planned when the first 40 subjects in Group A have been treated and have been evaluated for response or have permanently discontinued study treatment because of disease progression, withdrawal of consent, or death. Group A of the study will be terminated for futility if ≤ 13 of the 40 subjects have responded (ie, CR/CMR or PR/PMR) based on assessments provided by the IRC; otherwise the study will continue. A timely assessment of response will be performed to avoid the risk of overenrollment.

An IDMC will be charged with evaluating interim futility results. The IDMC will consist of clinicians and an independent statistician. The IDMC will make recommendations to the sponsor at the planned interim futility analysis in Group A. The process by which the IDMC will make recommendations and decisions will be documented in the IDMC charter. Additional operational details of the interim analyses, including tables, figures, and listings provided to the DMC, will be provided in the DMC Charter.

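### The stated 90% chance that the 95% CI lower bound for ORR reaches 35% is 86.4% under the two-sided exact interval the plan specifies

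*Protocol*

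**What the plan says.** Protocol 9.2 sets Group A at 100 subjects and justifies the number in one sentence: "If the true ORR is 0.50, then there is approximately 90% probability of observing the lower bound of the 95% CI of the ORR" is 35% or higher. SAP 3.3 gives the same sentence. The Sample Size entry in the Protocol Synopsis is nearly identical: "If the true ORR is 0.50, then there is about 90% probability of observing the lower bound of the 95% confidence interval of" the ORR being at least 35%.

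The interval is defined elsewhere in the documents:

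- **Sidedness.** Protocol 9.3 and SAP 3.2 both say: "Within each group, 2-sided 95% CIs will be reported for all analyses when appropriate".
- **Method.** Protocol 9.4.1.1 and SAP 7.2.2 both say: "The ORR as determined by the IRC and its 95% exact binomial CIs will be calculated for subjects in Group A". The Synopsis also names the exact binomial interval for the primary analysis.
- **Denominator.** SAP 7.2.2 keeps subjects without adequate response data in the denominator, so the base is the full 100.

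There is one interim look. SAP 9.1 says: "Group A of the study will be terminated for futility if ≤ 13 of the 40 subjects have responded". Protocol 9.5 adds that "the IDMC will make recommendations to the sponsor at the planned interim futility analysis in Group A".

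Neither document gives the responder count behind the 90%, or says whether the 90% allows for the interim. The Amendment 1 log in Protocol Appendix C says only that "Section 9.2 (Selection of Sample Size) was updated to be consistent with the numbers used in the added interim analysis".

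**The concern.** The sample-size sentence can be checked entirely from the documents: n, the assumed ORR, the threshold, the confidence level, the sidedness and the method are all given. Put together, they do not return 90%.

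This matters because the sentence is the only account of what 100 subjects deliver for the primary endpoint. SAP section "7.1. Efficacy Hypotheses" is marked not applicable, so no power statement for a test stands beside it. Anyone judging whether 100 subjects are enough relies on this one probability, and it overstates what the design achieves.

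**Working it through.** **Inputs**

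| Input | Value | Source |
|---|---|---|
| Subjects, Group A | n = 100 | Protocol 9.2, SAP 3.3 |
| Assumed true ORR | p = 0.50 | Protocol 9.2, SAP 3.3 |
| Lower-bound threshold | 35%, inclusive | Protocol 9.2, SAP 3.3 |
| Confidence level | 95%, two-sided (0.025 in the lower tail) | Protocol 9.3, SAP 3.2 |
| Method | Exact binomial (Clopper-Pearson) | Protocol 9.4.1.1, SAP 7.2.2 |
| Futility rule | Stop if 13 or fewer of 40 respond | Protocol 9.6, SAP 9.1 |

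**Step 1: reproduce the stated 90%.** With X ~ Binomial(100, 0.50), P(X ≥ 44) = 0.9033. A cut-off of 44 responders therefore gives the plan's figure. With the futility rule binding, the same cut-off gives 0.8959.

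**Step 2: does 44 meet the criterion?** The two-sided exact lower bound for x responders is the 0.025 quantile of Beta(x, n − x + 1).

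- x = 44: Beta(44, 57) gives 0.3408, below 0.35.
- x = 45: Beta(45, 56) gives 0.3503, at or above 0.35.

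At least 45 responders are needed.

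**Step 3: probability under the specified interval.** P(X ≥ 45) = 0.8644. The shortfall is 90 − 86.4 = 3.6 points, and the miss probability is 100 − 86.4 = 13.6%.

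**Step 4: add the interim as a binding rule.** Sum over a = 14 to 40 of P(X₄₀ = a) × P(X₆₀ ≥ 45 − a), where X₄₀ and X₆₀ are the responders among the first 40 and the remaining 60. The result is 0.8587. The shortfall is 90 − 85.9 = 4.1 points, and the miss probability is 14.1%. The rule stops Group A with probability P(X₄₀ ≤ 13) = 0.0192 at p = 0.50. Only 0.0056 is lost from the probability of reaching 45, because most stopped trials would have fallen short anyway.

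**Step 5: would another interval give 90%?**

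| Calculation | Responders needed | Probability at p = 0.50 |
|---|---|---|
| Two-sided exact (as specified) | 45 | 86.4% |
| Two-sided Wald, Wilson, Agresti-Coull, Jeffreys or mid-p | 45 | 86.4% |
| Two-sided Wald with continuity correction | 46 | 81.6% |
| Normal approximation (null or alternative variance in the bound) | – | 87.1% or 85.1% |
| Arcsine approximation | – | 86.1% |
| One-sided 95% exact or Wald | 44 | 90.3% |
| Two-sided Wilson or Jeffreys, bound rounded to a whole percent | 44 | 90.3% |
| One-sided 95% Wilson, Agresti-Coull or Jeffreys | 43 | 93.3% |

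The one-sided 95% exact bound at 44 responders is 35.56%, which passes; at 43 it is 34.60%, which does not. Rounding the specified two-sided exact bound to a whole percent still requires 45.

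**Step 6: scale of the gap.** With 45 required out of 100, the probability reaches 90% at a true ORR of 0.509 (no interim) or 0.510 (binding rule). Holding the true ORR at 0.50 with no interim, 90% is first reached at n = 115 (51 responders, 90.4%).

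**The case against.** Four points can fairly be made for the plan.

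*The figure is hedged.* All three places present 90% as approximate, and the gap comes from a single responder: P(X = 44) is 0.9033 − 0.8644 = 3.9 points. Even so, 86.4% would not normally be rounded to 90%, and a miss probability of 13.6% is more than a third above 10%.

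*The sample-size sentence does not itself say two-sided or exact.* In Protocol 9.2 and SAP 3.3 those properties come from neighbouring sections. That is correct, but they are the only interval properties the documents give, and no unrounded two-sided method tried reaches 90%.

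*Nothing planned depends on the 35% bound.* This stands in full. The primary analysis is an estimate with an interval, no efficacy hypothesis is set, and the futility boundary is specified separately. It limits the seriousness of the error but does not make the figure right.

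*The 85.9% assumes that the futility rule is always followed*, whereas the monitoring committee makes recommendations to the sponsor. This also stands: 85.9% should be labelled as the binding case. It differs from 86.4% by only 0.6 points, so the conclusion is the same on either reading.

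The documents do not say where the 90% came from. A one-sided 95% bound is one possible source and rounding a non-exact bound is another. Both are inference.

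**Conclusion.** The stated probability is wrong as written. Under the two-sided exact 95% interval, with n = 100 and a true ORR of 0.50, it is 86.4% without the interim and 85.9% with the futility rule treated as binding. Allowing for the interim therefore cannot recover the 90%; it only lowers the figure slightly.

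The result assumes independent binomial responses with a common ORR and all 100 subjects in the denominator. The error is modest and confined to a design statement: no planned estimate, interval or stopping boundary changes. It should still be corrected, because it is the sole quantitative justification for the Group A sample size and appears three times.

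**What to change.** Replace the sentence in the Synopsis, Protocol 9.2 and SAP 3.3 with wording such as: If the true ORR is 0.50, there is about 86% probability (86.4% without the futility rule, 85.9% with it treated as binding) that the two-sided exact 95% CI has a lower bound of at least 35%, which requires at least 45 responders in 100.

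If the 90% was meant for a one-sided 95% bound, state that and reconcile it with Protocol 9.3 and SAP 3.2, which specify two-sided intervals.

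The cost is wording in three places and a slightly less favourable stated figure. Design, enrolment and analysis stay as they are.
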